#### Recommended Hepatic Discontinuation Criteria

Study drug should be discontinued permanently if one of the following occurs (as confirmed by repeat assessment) and if the event is without an alternative explanation:

- ALT or aspartate aminotransferase (AST)  $>8 \times$  ULN;
- ALT or AST  $>5 \times$  ULN for more than 2 weeks;

- ALT or AST  $>3 \times$  ULN and either total bilirubin  $>2 \times$  ULN or international normalized ratio  $>1.5$ ; and/or
- ALT or AST  $>3 \times$  ULN with the appearance of fatigue, nausea, vomiting, right upper quadrant pain or tenderness, fever, rash, and/or eosinophilia ( $>5\%$ ).

It is also recommended that statin regimen is discontinued. Abnormal values should be followed until they return within normal range or to a level deemed acceptable by the Investigator, or until the abnormality is explained by an appropriate diagnosis.

### 3 LIST OF ABBREVIATIONS AND DEFINITIONS OF TERMS

AE	adverse event
ALT	alanine aminotransferase
ANCOVA	analysis of covariance
ANGPTL4	angiopoietin like 4
Apo	apolipoprotein
AST	aspartate aminotransferase
ATC	anatomical therapeutic chemical
BMI	body mass index
BUN	blood urea nitrogen
CFBL	change from baseline
CRF	case report form
DPP	dipeptidyl peptidase
ECG	electrocardiogram
eCRF	electronic case report form
EOS	end of study
ET	early termination
FAS	Full Analysis Set
FPG	fasting plasma glucose
GFR	glomerular filtration rate
GGT	gamma-glutamyl transferase
HbA1c	hemoglobin A1c
HBV	hepatitis B virus
HCV	hepatitis C virus
HDL-C	high-density lipoprotein cholesterol
HIV	human immunodeficiency virus
HoFH	homozygous familial hypercholesterolemia
hsCRP	high-sensitivity C-reactive protein
IL-6	interleukin-6
LDL-C	low-density lipoprotein cholesterol
LOCF	last observation carried forward
LDL-TG	low-density lipoprotein triglyceride
Lp(a)	Lipoprotein(a)
MedDRA	Medical Dictionary for Regulatory Activities
NCEP ATP-III	National Cholesterol Education Program Adult Treatment Panel III
NGAL	neutrophil gelatinase-associated lipocalin
PCS	potentially clinically significant
PCSK9	proprotein convertase subtilisin/kexin type 9
PPS	Per-Protocol Set
PT	preferred term

QD	once daily
QTcB	QT interval corrected for heart rate with Bazett's formula
QTcF	QT interval corrected for heart rate with Fridericia's formula
SAA	serum amyloid A
SAE	serious adverse event
SAS	Safety Analysis Set
SBP	systolic blood pressure
SD	standard deviation
SOC	system organ class
TC	total cholesterol
TEAE	treatment-emergent adverse event
TG	triglyceride
TSH	thyroid-stimulating hormone
ULN	upper limit of normal
VLDL-C	very low-density lipoprotein cholesterol
WHO	World Health Organization

## **4 CHANGES IN CONDUCT AND PLANNED ANALYSES FROM THE PROTOCOL**

### **4.1 Unblinding After Last Patient Last Visit at Week 12**

The protocol states that the blind is not to be broken during the study unless considered necessary by the Investigator for emergency situations for reasons of subject safety. However, when the final subject has completed the double-blind portion of the study (ie., the Week 12 visit), the process of unblinding will begin.

Once the last patient has completed the Week 12 visit, an unblinded team (separate from the study team) consisting of at least one unblinded statistician and one unblinded programmer will request the treatment codes, perform unblinding activities, and provide a subset of summary results to Gemphire. All data for subjects completed through Week 12 will be cleaned and frozen to facilitate delivery of the Week 12 results, and no results beyond Week 12 will be provided in this delivery. The final database lock will occur after the 4-week follow-up for all subjects as planned, and the remaining outputs will be delivered following database lock.

The study team will not be unblinded to individual subjects and will only be unblinded to select overall results at the treatment group level. Additional details regarding the specifics of who will be unblinded and when will be included in a separate memo, which will be finalized prior to the Week 12 unblinding.

### **4.2 Clarifications to Schedule of Procedures**

The schedule of procedures table in the protocol indicates that fasting lipid panel will be assessed at every study visit including the follow-up visit. However, fasting lipid panel will not be assessed at the follow-up visit.

### **4.3 Clarifications and Changes in Analyses**

The following list provides changes from the protocol reflected in the SAP:

- The protocol states that a parametric analysis of covariance (ANCOVA) will be completed for primary, secondary and exploratory endpoints; and that either the data would be transformed (and analyzed using ANCOVA) or that a non-parametric test would be used if the assumption of normality is violated. However for consistency with prior studies in hypertriglyceridemia, an ANCOVA on the ranked-transformed data will be considered the main analysis for these endpoints.
- Although the percent of diabetic subjects with > 5% decrease in dosage of anti-diabetes pharmacologic therapy from baseline to Week 12 was cited in the protocol as an exploratory endpoint, this analysis will not be conducted, as it was determined that this analysis would be inconclusive due to the way patients were recruited.
- Confirmatory analyses (using the per protocol set) for secondary and exploratory analyses were detailed in the protocol, but these will not be conducted.

- Sampling for ApoA-V was delayed and will be eliminated. Therefore, secondary and exploratory analyses for ApoA-V will not be performed.
- The protocol indicates that treatment, baseline statin stratum (yes or no), and baseline (covariate) will be included in the secondary and exploratory ANCOVA models as factors. However, as the qualifying TG stratum ( $> 880 \text{ mg/dL}$  and  $\leq 880 \text{ mg/dL}$ ) was a stratification factor for this study, it will also be included as a factor in all secondary and exploratory ANCOVA models for all parameters except Triglycerides (TGs).

## 5 INTRODUCTION

The purpose of this statistical analysis plan is to describe the framework for the reporting, summarization, and statistical analysis methodology of the safety and efficacy parameters measured throughout the study. It is based on Protocol GEM-401 Version 4.0 dated 17 Mar 2017.

## 6 STUDY OBJECTIVES AND ENDPOINTS

### 6.1 Objectives

#### 6.1.1 Primary Objective

The primary objective of this study is to assess the effect of gemcabene 300 mg and 600 mg once daily (QD) compared to placebo on fasting serum TG levels after 12 weeks of treatment in subjects with severe hypertriglyceridemia ( $\geq 500 \text{ mg/dL}$  to  $< 1500 \text{ mg/dL}$ ) on a self-reported, stable, heart-healthy diet.

#### 6.1.2 Secondary Objectives

The secondary objectives of this study are the following:

- To assess the safety and tolerability of gemcabene 300 mg and 600 mg QD in subjects with severe hypertriglyceridemia;
- To assess the effect of gemcabene 300 mg and 600 mg QD on other lipid and apolipoprotein parameters, high-sensitivity C-reactive protein (hsCRP), interleukin-6 (IL-6), serum amyloid A (SAA), angiopoietin like 4 (ANGPTL4), adiponectin, and fibrinogen after 12 weeks of treatment.

#### 6.1.3 Exploratory Objectives

The exploratory objectives are the following:

- CI

- CI [REDACTED]

## 6.2 Endpoints

### 6.2.1 Primary Endpoint

The primary efficacy endpoint is the percent change in fasting serum TG from baseline to end of study (EOS).

### 6.2.2 Secondary Endpoints

The secondary endpoints are as follows:

- Change and percent change from baseline to Weeks 2, 6, 10, and 12 in fasting serum TG, and change from baseline to EOS in fasting serum TG;
- Change and percent change from baseline to Weeks 2, 6, 10, 12, and EOS in total cholesterol (TC), non-high-density lipoprotein cholesterol (non-HDL-C), HDL-C, and very low-density lipoprotein cholesterol (VLDL-C);
- Change and percent change from baseline to Weeks 10, 12, and EOS in apolipoprotein (Apo) B, ApoA-I, ApoA-II, ApoC-II, ApoC-III, and ApoE;
- Change and percent change from baseline to Weeks 10, 12, and EOS in low-density lipoprotein cholesterol (LDL-C) (ultracentrifugation), low-density lipoprotein triglyceride (LDL-TG), VLDL-TG, HDL-TG;
- Change and percent change from baseline to Week 12 in lipoprotein size and particle number (NMR);
- Change and percent change from baseline to Weeks 10, 12, and EOS in hsCRP, IL-6, SAA, adiponectin, and fibrinogen; and
- Percent of subjects achieving a TG value < 500 mg/dL (5.65 mmol/L) at Weeks 10, 12, and EOS.
- Secondary endpoints related to safety include adverse events (AEs), safety laboratory parameters (chemistry including cystatin-C, hematology, coagulation values); urinalysis including urine protein:creatinine ratio, urine albumin:creatinine ratio and neutrophil gelatinase-associated lipocalin (NGAL); vital signs, electrocardiogram (ECG) results; and physical examinations (PEs).

### 6.2.3 Exploratory Endpoints

The exploratory efficacy endpoints are as follows:

- CI [REDACTED]

- CI [REDACTED]
- [REDACTED]

Appendix 3 contains anatomical therapeutic chemical (ATC) categories and descriptions that will be used to identify anti-diabetes pharmacologic therapy for subjects. If an anti-diabetes pharmacologic therapy has a start date on or before first dose of study drug (ie, medication start date less than, or equal to day of first dose of study drug) and a stop date on or after first dose of study drug (ie, medication stop date greater than, or equal to day of first dose of study drug) it will be used in analysis. Partial and missing dates will be imputed using rules in Appendix 2.

## 7 STUDY DESIGN CONSIDERATIONS

### 7.1 Study Design

This is a Phase 2, randomized, double-blind, parallel-group, multi-center study. Total study duration will be up to 26 weeks with 12 weeks of study drug treatment. The study will consist of a Pre-Screening Visit (only for subjects requiring a wash-out period), up to 3 Screening Visits, a 12-week Treatment Period (with 5 Visits), and a Follow-up Visit (4 weeks after the last dose).

**Table 1. Overview of Study Periods**

	Wash-out Period (for subjects requiring wash-out)	Screening Visit	Treatment Period
Study Days	Day -84 to -29, inclusive	Day -28 to -1, inclusive	Day 1 to 85, inclusive

Approximately 90 subjects with severe hypertriglyceridemia (TG  $\geq$  500 mg/dL to < 1500 mg/dL) will participate in the study from approximately 40-50 sites in the United States and Canada.

**Pre-Screening (Wash-Out Period):** A wash-out period will be required for potential subjects taking any lipid-regulating therapies or supplements, with the exception of statins or ezetimibe 10 mg QD. Subjects may initiate the wash-out period, if meeting all other criteria and have a qualifying fasting TG value of  $\geq$  350 mg/dL. For subjects requiring a wash-out period, the Pre-Screening Visit will be their first study visit and will occur anywhere from 4 to 8 weeks prior to the Screening Visit (S1, Week -4) based on the type of lipid-regulating therapy and its associated duration of wash-out required.

The duration of the wash-out period will be dependent upon the status of the subject's current lipid-regulating therapy. Specifically, proprotein convertase subtilisin/kexin type 9 (PCSK9) inhibitors will require an 8-week wash-out period, fibrates will require a 6-week wash-out period, and niacin, OMG-3 compounds, bile acid sequestrants or other lipid-regulating therapies will require a 4-week wash-out period prior to the Screening Visit. If the subject needs to be washed off more than one lipid-altering medication, the medication that requires the longest washout period will be the default. If a potential subject is statin-naïve, or dosing only on a statin or ezetimibe (for at least 12 weeks) and not currently dosing on other lipid-altering medications, there is no requirement for a Pre-Screening Visit.

During this wash-out period, potential subjects will be counseled on the importance of maintaining a heart-healthy diet and limiting alcohol intake.

**Screening Period:** All potential subjects will participate in the Screening Period, including Screening Visit 1 (S1), Screening Visit 2 (S2) and, if necessary as outlined below, optional Screening Visit 3 (S3) up to 28 days prior to Study Day 1 (Visit T1). For potential subjects on stable statin therapy and/or ezetimibe for  $\geq 12$  weeks who do not require a wash-out period, S1 will be their first study visit. For other subjects who have been washing out their other lipid medications, S1 occurs after the full required washout has been completed.

During this Screening Period, potential subjects must meet the TG qualifying values in order to be eligible for randomization on Day 1 (Visit T1).

At the end of this 2-4-week diet and lifestyle stabilization and TG qualifying period, eligible subjects must have an average fasting TG level  $\geq 500$  mg/dL to  $< 1500$  mg/dL in order to qualify for the 12-week double-blind treatment period. The TG level for qualification will be based on the average (arithmetic mean) of the Visit S1 and Visit S2 values. If a subject's average TG level from Visit S1 and Visit S2 falls outside the required range for entry into the study, one additional sample for fasting TG value can be collected 1 week later (at the Optional Visit S3), and the arithmetic mean from Visits S2 and S3 will then be used to determine eligibility.

**Double-Blind Treatment Period:** Eligible subjects will be randomized on Day 1 via an interactive web/voice response system (IWRS/IVRS) on Study Day 1 in a 1:1:1 ratio (30 subjects per group) to one of the following treatment groups:

- Gemcabene 300 mg QD, or
- Gemcabene 600 mg QD, or
- Placebo

Subjects will be stratified by baseline statin therapy (yes or no) and qualifying TG value ( $< 880$  mg/dL or  $\geq 880$  mg/dL) to ensure background therapies and baseline TG values are balanced across all treatment groups.

The Follow-up Visit will occur 4 weeks ( $\pm 3$  days) after the last dose of study drug.

## 8 ANALYSIS POPULATIONS

### 8.1 Full Analysis Set

The Full Analysis Set (FAS) will consist of all randomized subjects who receive at least 1 dose of study drug and have at least 1 post-baseline efficacy assessment. All subjects in the FAS will be analyzed based on their randomized treatment group, regardless of the treatment they actually received. The FAS population will be the primary analysis population. All efficacy analyses will be performed on the FAS.

## **8.2 Per-Protocol Set**

The Per Protocol Set (PPS) will be determined partially through sponsor review of blinded individual subject data and partially through objective criteria. Both methods will be completed prior to database lock. The following criteria for FAS subjects should be met in order to qualify for the PPS:

- Subjects completed the 12-week Treatment Period
- Subjects taking a statin in combination with study drug did not experience a change or interruption in statin dose
- Subjects took the same study drug medication for the entire study duration and it matches the treatment to which they were randomized

Additionally, a sponsor review for any other major protocol deviations that may impact efficacy (such as low study medication compliance [i.e., approximately 80% or lower] after Week 6) will be conducted, and further subjects could be excluded from the PPS. The PPS will be used to assess robustness of the analysis results. Subjects excluded from the PPS and the reason for exclusion will be provided in the listings.

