### 12.1 Adverse Events

AEs will be coded using Medical Dictionary for Regulatory Activities (MedDRA) version 19.1. All AE tables will be summarized for overall by treatment group and by stable statin use at baseline (according to the CRF) within treatment group. Except for the AE overview table and summaries of serious adverse events (SAEs) and AEs resulting in death (both of which will include all AEs), AE tables will only include summaries of treatment-emergent adverse events (TEAEs). A TEAE is defined as an AE with start date on or after the first dose date and less than 30 days after the last dose date. If AE start date is missing, the AE is assumed to be a TEAE. An AE overview table containing the frequency and percent of the following will be summarized by treatment group, and treatment group within each baseline statin (yes or no):

- Number of subjects with at least one TEAE, drug-related TEAE, SAE, drug-related SAE;
- Number of subjects who discontinued study treatment due to TEAE, drug-related TEAE, SAE, and drug-related SAE;
- Number of subjects who discontinued the study due to a TEAE; and
- Number of subjects who had a study treatment interruption due to a TEAE;
- Number of deaths and deaths due to a drug-related TEAE.

Additionally, the following will be summarized by treatment group, and treatment group within each stratum:

- TEAEs by system organ class (SOC) and preferred term (PT);
- TEAEs by descending PT ;
- TEAEs by SOC, PT, and maximum severity;
- Related TEAEs by SOC and PT;

- Related TEAEs by descending PT;
- SAEs by SOC and PT;
- Related SAEs by SOC and PT;
- TEAEs leading to treatment discontinuation by SOC and PT;
- Related TEAEs leading to treatment discontinuation by SOC and PT; and
- AEs that resulted in death by SOC and PT.

Summaries of SOC and PT will be sorted alphabetically by SOC and by decreasing frequency of PT in the total column for the gemcabene 600 mg group, followed by the 300 mg group, then placebo.

Note that the overview of AEs will be provided separately for the double-blind treatment period and follow-up period, to allow for a delivery of the double-blind data only during the database freeze.

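### The per-protocol set need only be settled before database lock, but SAP 4.1 gives the sponsor treatment-group Week 12 results before lock

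*SAP*

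**What the plan says.** SAP 8.2 lists three criteria for the PPS: completing the 12-week treatment period, no change or interruption of statin dose for subjects taking one, and taking throughout the same study drug as randomized. It then adds a sponsor review that can exclude further subjects for "any other major protocol deviations that may impact efficacy (such as low study medication compliance [i.e., approximately 80% or lower] after Week 6"). The review uses blinded individual subject data. On timing it says only: "Both methods will be completed prior to database lock". Protocol 9.2.2 and the protocol synopsis also name database lock and nothing earlier.

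SAP 4.1 describes a staged unblinding. After the last Week 12 visit, a team separate from the study team "will request the treatment codes, perform unblinding activities, and provide a subset of summary results to Gemphire". For this step, "All data for subjects completed through Week 12 will be cleaned and frozen to facilitate delivery of the Week 12 results". Lock comes later: "The final database lock will occur after the 4-week follow-up for all subjects as planned". On who learns what: "The study team will not be unblinded to individual subjects and will only be unblinded to select overall results at the treatment group level". A separate memo gives details of who is unblinded and when, "which will be finalized prior to the Week 12 unblinding". SAP 12.1 is consistent with this order: it splits the adverse event overview by period "to allow for a delivery of the double-blind data only during the database freeze".

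SAP 11.2 uses the PPS for one of two sensitivity analyses of the primary endpoint. SAP 4.3 drops the PPS runs for secondary and exploratory endpoints.

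**The concern.** A deadline of database lock protects a per-protocol population when nobody has seen results before lock. That held under Protocol 5.4, which allows the blind to be broken during the study only in emergencies. SAP 4.1 openly departs from that rule by starting to unblind after the last Week 12 visit, but SAP 8.2 keeps lock as the milestone. Lock no longer guarantees that PPS decisions precede the results.

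This matters because part of PPS membership is a judgement. What counts as another major deviation that may affect efficacy is open-ended, and low compliance is only an example. SAP 8.2 says the PPS is there to assess robustness. That check carries less weight if the people deciding who is excluded could already know how the arms compare.

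**Working it through.** No figure in the plan is at issue, and the sample-size calculation in SAP 9.1 does not enter. The check is one of sequence.

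**1. Order of events under SAP 4.1**

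- (a) The last subject completes Week 12.
- (b) Data through Week 12 are cleaned and frozen, the separate team obtains the codes, and a subset of summary results goes to the sponsor.
- (c) The 4-week follow-up is completed for all subjects.
- (d) The database is locked.
- (e) The remaining outputs are delivered.

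The PPS deadline in SAP 8.2 and Protocol 9.2.2 is (d). Nothing ties PPS membership to (a) or (b).

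**2. Length of the interval for the last subject**

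- Target days in the schedule (Protocol Appendix A): Week 12 is Study Day 85 and follow-up is Study Day 113, so 113 − 85 = 28 days.
- Follow-up is timed from the last dose, 4 weeks ± 3 days. If the last dose is on the visit day (assumption), follow-up is 28 ± 3 = 25 to 31 days after the visit. If it is the day before (assumption), it is 27 ± 3 = 24 to 30 days.
- Lock comes after that. The date of the Week 12 delivery is not given, so the time for which the sponsor would hold results before lock is unknown.

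**3. Which parts of the PPS leave room for judgement**

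- Completion and statin change are objective and need no treatment codes.
- The match between drug taken and randomized treatment is objective but needs the codes, so it cannot be closed before they are released.
- The sponsor's review of other major deviations is a judgement. This is the exposed part.

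**4. Whether other text closes the gap**

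- The freeze covers data through Week 12. The SAP does not say that it covers the classification of deviations or PPS membership.
- Hiding individual allocations does not hide group results. SAP 4.1 says the study team will see some of them.
- The memo covers who is unblinded and when. The SAP does not say that it sets a PPS deadline.
- The listing of excluded subjects gives the reason for each exclusion, not the date of the decision.

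**5. What depends on the PPS**

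- Only the PPS rerun in SAP 11.2. The primary analysis and the lowest-rank sensitivity analysis use the FAS, whose definition in SAP 8.1 involves no deviation review.

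**The case against.** The strongest reply is that the safeguards already do most of the work. The review must use blinded individual data, the codes go to a separate team, the underlying Week 12 data are frozen, and every exclusion is listed with its reason. Someone who knows only group results cannot read from the record which arm an exclusion would affect. The memo, which is not among the documents, may separate the reviewers from those who receive results, or may set an earlier cut-off. The protocol's deadline is no separate fault either, because the protocol foresaw no unblinding at Week 12.

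Most of this stands, and it limits the weight of the point. It does not remove it. The sponsor carries out the review and the sponsor receives the results, and SAP 8.2 does not say that triglyceride values are withheld from the reviewers. The only stated deadline still falls after the results are released.

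A reader might infer more than the text supports, in three ways:

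- **That the sponsor planned to choose the PPS after seeing results.** The text permits that order. It does not show that it was intended or that it happened.
- **That the delivered subset contains the FAS triglyceride result or the PPS rerun.** SAP 4.1 does not list the contents.
- **That the risk can be sized from tablet counts around the 80% compliance figure, or from the share of an arm that one exclusion represents.** SAP 10.3.1 derives compliance from the drug interruption form and also computes it at each visit, and visit days vary within their windows. Neither calculation would measure a bias.

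**Conclusion.** The point holds as a gap in timing. The text lets the sponsor's judgement-based exclusions be finalised after selected treatment-group results have reached the sponsor and before lock. Confidence is high that the text permits this order. The documents give no basis for saying how likely it was or which way it would move the result.

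The consequence is confined to one supportive analysis, the PPS rerun of the primary endpoint. The FAS primary analysis, its power, its alpha and the lowest-rank sensitivity analysis are untouched. The weight of the point depends on two things the documents leave open: whether the delivered subset includes the primary triglyceride comparison, and whether the memo sets an earlier sign-off. If the memo does, the change below only records existing practice in the SAP. The change should be made because it is cheap and restores the purpose of the deadline. The trial's main conclusion does not depend on it.

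**What to change.** In SAP 8.2, replace the sentence that sets the database-lock deadline with:

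> The sponsor's blinded review and the completion and statin-change criteria will be finalised and signed off, with reasons, before treatment codes are requested for the Week 12 delivery (Section 4.1). The only later change to the PPS will be the programmed application, by the separate unblinded team, of the criterion that study drug taken matches the randomized treatment. Any other deviation identified after the code request will be documented and handled only in an additional analysis labelled as post-unblinding.

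Add a cross-reference in SAP 4.1. Protocol 9.2.2 need not change: earlier sign-off meets its deadline, and that deadline still applies to the programmed step.

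The cost is one sentence becoming three, one cross-reference, and a review held earlier, around the Week 12 data freeze. No extra data are needed. The real downside is that a genuine deviation found late, other than a treatment mismatch, stays in the main PPS run and is dealt with only in the labelled additional analysis.
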